5.3.8. Exploratory Analyses of Immunogenicity Data

Due to the impact of the COVID-19 pandemic on clinic visit schedules, a protocol amendment extended the range in which booster vaccinations are given from 9 (+1) months to 9-18 (+1) months of age. The change enables the study to explore the effect of the length of time between completion of the primary series and administration of the booster dose on post-booster responses and booster effects. We will use log-linear models to explore the effect of time between V4 and V5 on post-booster IgG and OPA responses in each treatment group (GMCs and GMTs), and log-linear random effects models to explore the effects of time on booster responses (GMC and GMT ratios). Generalized linear models with logit link will be used to explore the corresponding effects of time on post-booster seroresponse rates (IgG concentrations ≥ 0.35 $\mu\text{g/mL}$; IgG concentrations ≥ 1 $\mu\text{g/mL}$; OPA titer ≥ 8). Analyses will be restricted to the Primary Per Protocol Immunogenicity Population. All results will be reported as exploratory in nature using descriptive 95% CIs and p-values.

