6	Vital signs and PE (targeted after screening)*	✓^✓	✓	✓^✓	✓	✓^✓	✓
7	Blood sample for immunogenicity testing				✓	✓@	✓
8	Rapid malaria diagnostic test*	✓	✓	✓		✓	
9	Eligibility check*	✓	✓	✓		✓	
10	Assign randomization ID	✓					
11	Study vaccination	✓		✓		✓	
12	EPI vaccination	✓	✓	✓		✓ ^a	
13	Record local/systemic solicited reactions	✓		✓		✓	
14	Record adverse events (including SAE)*	✓	✓	✓	✓	✓	✓
15	Record concomitant medications*	✓	✓	✓	✓	✓	✓
16	Schedule/confirm next visit	✓	✓	✓	✓	✓	✓
17	Exit study [†]						✓

Age ranges indicated for V1/V5. Other vaccination/follow up visits to be scheduled at 4 weeks post prior visit + 2 week window.

* If screening extends beyond 1 clinic visit assessments (*) need to be repeated on the day of randomization/1st vaccination.

@Blood sample to be collected prior to administration of booster dose

#EPI vaccination visit; ~Confirmation of medical history; ^ Evaluations will be conducted twice – before and after vaccination

^a Except for subjects who receive the EPI vaccines earlier than the study booster dose due to impact of the COVID-19 pandemic

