Secondary Objective 5 is to evaluate the persistence of serum IgG antibody responses to the 10 serotypes in PNEUMOSIL at 9-18 months of age, prior to the booster dose. The percentage of responders (IgG $0.35 \mu\text{g/mL}$) and GMCs will be reported by PNEUMOSIL serotype and treatment group, together with 95% CIs. Serotype-specific differences in response rates (PNEUMOSIL vs. each comparator) and GMC ratios will be reported with 95% CIs.

Secondary Objective 6 is to evaluate – in a subset of subjects in the Primary PP_IMM Population – the persistence of functional antibody responses to the 10 serotypes in PNEUMOSIL as measured by OPA at 9-18 months of age, prior to the booster dose. The proportion of subjects with serotype-specific serum OPA titers $\geq 1:8$ and GMTs will be reported by PNEUMOSIL serotype and treatment group, together with 95% CIs. Serotype-specific differences in response percentages (PNEUMOSIL vs. each comparator) and GMT ratios will be reported with 95% CIs.

Secondary Objective 7 is to evaluate booster responses (serum IgG concentrations and functional responses) from 4 weeks after the primary series (V4) to 4 weeks post booster dose (V6). For each PNEUMOSIL serotype, the ratio of post-booster to post-primary series IgG GMCs and OPA GMTs will be reported by treatment group with 95% CIs, restricted to subjects who provide response data at both V4 and V6.

In addition to the summary measures of immunogenicity responses described above for each of the primary and secondary objectives, reverse cumulative IgG concentration and OPA titer distribution curves will be presented by serotype and treatment group.

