3.1. Visit Schedule and Evaluations

Study vaccinations will be scheduled to occur at 6 weeks of age (+2 week visit window; Visit 1 [V1]), 14 (+2) weeks of age (V3), and 9-18 (+1) months of age (V5). Standard Expanded Program on Immunization (EPI) vaccinations in The Gambia (except Prevenar 13) will be given concomitantly with each primary dose of study vaccine, at 10 (+2) weeks of age (V2), and at 9 months of age where reasonable (recognizing the impact of SARS-CoV-2 on the feasibility of clinic visits). Blood draws for immunogenicity assessments will occur 4 (+2) weeks after the second study vaccination (V4), immediately prior to booster vaccination (V5) at 9-18 months of age, and at 4 (+2) weeks after booster vaccination (V6), which serves as the end-of-study visit. All subjects with evaluable specimens will be assessed for serum IgG responses. For functional antibody responses, 50 subjects who completed V4 per protocol and intended to continue to V6

were selected from each treatment group for OPA specimen testing. Subjects who did not complete V5 or V6 per protocol were replaced with new subjects from the same field site and treatment group to contribute V5 and V6 OPA data (see Section 3.5). The study schema is presented in Table 1.

Table 1. Study Schema

Visit / Age (with length of visit window in parentheses)					
V1	V2	V3	V4	V5	V6
6 (+2) wks	10 (+2) wks	14 (+2) wks	V3+4 (+2) wks	9-18 (+1) mo	V5+4 (+2) wks
X, E	E	X, E	B	B, X, E	B

wks = weeks, mo = months, X = study vaccination, E= EPI vaccines, B = blood sample for immunogenicity testing

Solicited reactogenicity events (REs) and vital signs will be assessed at 30 (+/- 10) minutes following each study vaccination. Solicited local REs include tenderness, erythema/redness, and induration/swelling at the injection site. Solicited systemic REs include cutaneous rash, fever, irritability, drowsiness, and decreased appetite. In addition to in-clinic assessments on the day of vaccination, all subjects will be monitored by field workers for local and systemic reactogenicity events during the 6 days after each study vaccination administration.

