3.9. Covariates

Unless otherwise noted, no covariates will be utilized in primary or secondary statistical analyses of immunogenicity, safety, or tolerability. An exploratory analysis of the effect of duration of elapsed time between completion of the primary series and booster vaccination on post-booster responses and booster effect will be performed, and this analysis may control for covariates such as gender and field site. Additional post hoc analyses which explore the effects of covariates on immune responses may also be conducted.

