5.3.5. Secondary Objective 5: persistence of post-primary IgG responses

Secondary objective 5 is to evaluate the persistence of the post-primary serum IgG antibody responses (seroresponse rates and GMCs) to the 10 serotypes in PNEUMOSIL, alone and in comparison to IgG antibody responses to these serotypes induced by Prevenar 13 and Synflorix, at 9 months of age (prior to a booster dose). For each serotype, the proportion of IgG antibody responders (IgG concentrations $\geq 0.35 \mu\text{g/mL}$) and the GMC at V5 (just prior to booster) will be reported, together with 95% CIs for the proportions and GMCs. Differences in seroresponse rates and GMC ratios (PNEUMOSIL versus each comparison group) will also be reported with 95% CIs. Differences between groups will be considered statistically significant if the 95% CI excludes 0.0 (for response rates) or 1.0 (for GMCs).

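### The V5 persistence results pool children about 4 to 15 months after V4, no planned elapsed-time model covers them, and the SAP partly labels them as 9-month results

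*SAP*

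**What the plan says.** Objectives 5 and 6 concern persistence, in each arm alone and in comparison. Protocol 12.7.2 states Objective 5 as being to "evaluate the persistence of serum IgG antibody responses to the 10 serotypes in PNEUMOSIL at 9-18 months of age, prior to the booster dose"; Objective 6 is the OPA counterpart in 50 subjects per group. SAP 2.1.2 gives the same 9-18 month range. The endpoints are defined only as measured before the booster.

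SAP 3.1 places V5 at 9-18 months of age with a one-month window and draws the sample immediately before the booster. SAP 3.7 analyses by nominal visit and does not reclassify by actual draw time unless blinded review decides otherwise. For each serotype, SAP 5.3.5 says that the responder proportion and "the GMC at V5 (just prior to booster) will be reported", giving one figure per arm.

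SAP 5.3.5 and 5.3.6 restate the two objectives as persistence at 9 months of age, not 9-18 months.

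Elapsed time is treated as exploratory. SAP 3.9 says that an analysis of the time from primary series to booster "on post-booster responses and booster effect will be performed". SAP 5.3.8 specifies it: log-linear models to "explore the effect of time between V4 and V5 on post-booster IgG and OPA responses in each treatment group", random-effects models for booster ratios, and logit models for post-booster seroresponse, all in the Primary PP_IMM Population.

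**The concern.** The pre-booster level is the measurement that elapsed time affects most directly, yet no planned elapsed-time model has it as an outcome. The protocol's own background (1.8.2) shows why this matters. In VAC-017, after a three-dose series, IgG GMCs fell substantially between the post-primary and pre-booster samples. They fell further in the Prevenar 13 group for the serotypes where that group had started higher.

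A pooled V5 GMC, GMT or seroresponse rate is therefore an average over whatever mix of ages the study suspension produced. A reader who wants to know how much antibody remains at a stated age cannot recover it from that average. If arms wane at different rates, the between-arm ratio also depends on the gap, and the pooled ratio does not show how. The 9-month wording adds a labelling risk: a table that includes children up to 19 months old could be headed as 9-month persistence.

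**Working it through.** **Inputs.** V3 is at 14-16 weeks of age and V4 is 4 (+2) weeks after V3 (SAP 3.1), so V4 falls at 18-22 weeks. V5 is at 9-18 (+1) months, so 9-19 months. One month = 365.25/12/7 = 4.348 weeks, so V4 is at 18/4.348 = 4.14 to 22/4.348 = 5.06 months.

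**The plan's own figures.** Two bear on this.
- Follow-up from randomisation to four weeks after the booster (Protocol Summary) is given as about 37 to 73 weeks, excluding windows. The minimum reproduces: 9 × 4.348 − 6 + 4 = 37.1. The maximum does not: 18 × 4.348 − 6 + 4 = 76.3. The stated 73 equals 37 + 9 × 4, that is, nine further months of four weeks each. This is a separate minor slip and does not affect the point.
- The GMC ratio precision in Protocol Table 17 reproduces. With CV 1.5 and n = 198 per group, SD(ln) = √ln(1 + 1.5²) = 1.086, and the 95% CI around a ratio of 1 is 0.81-1.24.

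**Permitted V4-V5 gap (months).**
- Nominal visits: 9 − 4.14 = 4.9 to 18 − 4.14 = 13.9.
- With the stated windows: 9 − 5.06 = 3.9 to 19 − 4.14 = 14.9.
- Protocol Table 14 has a looser rule, "Other vaccination/follow up visits to be scheduled at 4 weeks post prior visit + 2 week window". Chained from V1 at 8 weeks, it allows V4 at 8 + 6 + 6 + 6 = 26 weeks (5.98 months), which lowers the minimum to 3.0.
- If the 9-month wording of SAP 5.3.5 and 5.3.6 applied with a one-month window: 3.9 to 10 − 4.14 = 5.9, a span of 2 months instead of 11.

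**Effect on a within-arm GMC (illustration only).** The documents give neither a decay rate nor a booster-age distribution. Assume log-linear decay with half-life h months. A child sampled at 18 months then has 2^(−9/h) of the 9-month level: 0.13, 0.35 or 0.59 for h = 3, 6 or 12. If a fraction p of the arm is sampled at 18 months and the rest at 9, the pooled GMC is 2^(−9p/h) of the 9-month GMC:

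| p | h = 3 | h = 6 | h = 12 |
|---|---|---|---|
| 0.10 | 0.81 | 0.90 | 0.95 |
| 0.25 | 0.59 | 0.77 | 0.88 |
| 0.50 | 0.35 | 0.59 | 0.77 |

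The age mix matters as much as the half-life.

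**Effect on the between-arm ratio (illustration only).**
- Equal decay and balanced timing leave the ratio unchanged on average and add only variance. With gaps uniform over 11 months and h = 3, the added SD(ln) is (ln 2/3) × 11/√12 = 0.73. The total is √(1.086² + 0.73²) = 1.31, and the CI widens from 0.81-1.24 to 0.77-1.30. At 12 months or more it barely changes.
- If the arms had half-lives of 6 and 12 months, the ratio of the faster-waning arm to the slower at age 18 months would be 2^(−9 × (1/6 − 1/12)) = 0.59 of its value at 9 months. The pooled ratio would show some shift from V4 but not this time course.

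**The case against.** The strongest reply is that the endpoint is defined, randomised and secondary, and that most children may have been sampled near 9 months.

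- **Definition.** A reader might infer that persistence here has no defined time point. The documents do not support that: it is the sample taken immediately before the booster, with a stated age range. What is missing is a fixed time since the primary series.
- **Range.** The 3.9 to 14.9 months is what the windows permit, not what is expected. Protocol 1.10 aims to complete boosters quickly and capture as many children as possible at 9 months. With few late boosters the pooled GMC stays near the 9-month value, as the first row of the table shows. This stands, and it is why the size is left open.
- **Comparison.** Randomisation stratified by field site should balance timing, and the precision loss is small. A reader might infer bias between arms; nothing in the documents supports that. A decay difference would still move the pooled ratio. Only its dependence on the gap is hidden.
- **Existing provisions.** SAP 4.1 reports the percentage with a pandemic-delayed booster by arm, SAP 5.3.7 plans graphs at V4, V5 and V6, and SAP 3.9 allows further post hoc covariate analyses. These help, but none links the gap to the V5 level, and the last is a permission rather than a plan.

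**Conclusion.** The concern holds in a limited form. The V5 results of Objectives 5 and 6 have no fixed time since the primary series, pool gaps that may range from about 3.9 to 14.9 months, and lie outside the planned elapsed-time models. SAP 5.3.5 and 5.3.6 contradict SAP 2.1.2 and the protocol on the age to which the result refers; those passages must be reconciled.

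The main effect is on within-arm GMCs, GMTs and seroresponse rates, and on seeing whether the between-arm ratio varies with the gap. Its size depends on two quantities that the documents do not give, so the factors of 0.35 to 0.95 in the table illustrate assumed half-lives and age mixes and are not estimates. A reader might go further and infer that the V5 results cannot inform a 9-month booster programme. That would need the booster-age distribution, which the documents do not give. The primary endpoint is unaffected. The study is descriptive, so this is a change that should be made but not one on which the trial's main conclusion turns.

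**What to change.** 1. In SAP 3.9 and 5.3.8, add V5 outcomes to the models already planned: log-linear models for V5 IgG and OPA, and logit models for V5 IgG ≥0.35 µg/mL and OPA ≥8, on time from V4 to V5, by arm. Run them in the Secondary PP_IMM Population, which SAP 3.8 assigns to Objectives 5 and 6, rather than the Primary PP_IMM Population to which 5.3.8 is restricted.
2. Beside the V5 tables, report the distribution of the V4-V5 gap, or of age at V5, by arm. Show V5 IgG results separately for children sampled within the pre-amendment 9 (+1) month window and for those sampled later. Split OPA only if numbers allow: its subjects were chosen in order of entry (SAP 3.5), so one stratum could be nearly empty. The later stratum still covers a wide age range, so the models carry most of the information.
3. Reconcile the age stated in SAP 5.3.5 and 5.3.6 with SAP 2.1.2.

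The cost is SAP wording and extra runs of planned models on data already collected. Subgroup intervals will be wider, especially for OPA, and the results should be labelled exploratory.

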5.4. Evaluation of Safety and Tolerability

In this document solicited adverse events identified in the 30 (+/-10) minutes after each study vaccination or during field visits in the first 6 days after each study vaccination are referred to as reactogenicity events (REs) to distinguish them from all other (unsolicited) AEs.

5.4.1. Safety Analysis: General Issues

Safety and tolerability of study vaccines will be evaluated using the following endpoints:

- Number and severity of solicited local and systemic REs through Day 6 after each vaccination
- Number, severity and relatedness of all unsolicited AEs until 9 months of age, and from booster vaccination through a 4-week follow-up period
- Number, severity, and relatedness of all serious adverse events (SAEs) through the entire study period

Analysis Population: All analysis of safety and tolerability will be performed using the Safety Population, with analysis of REs conducted within subsets of time contributed to the Safety Population as described below.

Generally, safety evaluations will be descriptive in nature, and observed differences will be evaluated for medical relevance. Any statistical tests of treatment-group differences in safety endpoints, including calculation of 95% CIs around treatment-group differences, are not adjusted for multiple testing and are provided solely as a guide to clinical and scientific judgment.

Clinical assessments (e.g. vital signs) will be summarized separately by baseline and scheduled measurement time point pre-vaccination, post-vaccination and at follow-up visits. Results from unscheduled visits will be included in listings. For ease of review, baseline results may be reported on the same table as post-randomization results.

5.4.2. Adverse events

The onset date will be compared to the date of 1st vaccination (Day 0) to determine if it is a TEAE. Adverse events are considered treatment emergent if (a) onset occurs on or after the date/time of first vaccination, or (b) an event with onset prior to the first vaccination but increases in severity after administration of the vaccination. Only TEAEs with onset on or before V6 (4-weeks post booster) will be included in the formal safety analysis, although listing will be provided of all other AEs that occur in subjects who are not in the Safety Population or are not treatment emergent.

Summary tables of TEAEs (overall and by onset within 28 days of each vaccination) will be presented with numbers of events, and numbers and percentage of subjects, with any: (a) TEAEs; (b) unexpected TEAEs; (c) serious TEAEs; (d) vaccine-related TEAEs; (e) vaccine-related SAEs; (f) TEAEs leading to discontinuation of the vaccination series; and (g) TEAEs leading to death. Treatment-group differences in percent of subjects will be compared for each category (a)-(f) using the Cochran-Mantel-Haenszel (CMH) test stratifying on field site (Fisher's exact tests will be used if the number of events is < 5 for at least one treatment group). The 95% CI around treatment-group differences (PNEUMOSIL versus each comparator) will also be reported using Miettinen-Nurminen Score-type intervals (if the event rate is 0% in each group, then two event records – one for each group – will be included and given a weight of 0.000001 to facilitate computation of the 95% CI).

The process for medical coding will be conducted according to the █ 360 SOP 06006 “Medical Coding of Clinical Study Data using MedDRA”. Unsolicited TEAEs will be summarized and grouped by MedDRA System Organ Class (SOC) and AE preferred term using MedDRA™ v22.0 or higher coding terminology, by treatment group and pooled across groups. A similar summary will be provided for non-serious TEAEs (pooling solicited and unsolicited events). Results will be displayed in order of decreasing frequency, both across SOC and within each SOC term. In addition, TEAE summaries will be provided by severity (mild, moderate, severe, or life threatening/death if any), and by relationship to study vaccine (Related, Unrelated), overall and according to onset within 28 days of each vaccination.

A listing of all TEAEs through V6 will be presented by treatment group and will include subject identifier, AE verbatim description, preferred term, SOC, duration, relatedness to product, seriousness, severity, outcome, and action taken with respect to the investigational product.

Because of the number of variables to be reported, TEAE listings may be produced in two parts, sorted in the same order and with the same key identifiers to allow easy cross-reference.

TEAE listings will be repeated for (a) those that were serious, severe (Grade 3 or 4), considered related to vaccine, or leading to discontinuation of the vaccination series, and (b) any events of special clinical interest (including unexpected events) identified in blind review.

The concomitant medication/drug/treatment verbatim text will be coded using a combination of Lexicomp and the on-line Physicians' Desk Reference. Concomitant medications will be tabulated using frequencies and percentages and listed.

Owing to the impact of COVID19 on clinic visit schedules, unsolicited AEs were not routinely collected after 9 months of age but before the booster dose (V5). Any AEs that are recorded in the database that have an onset after 9 months but before V5 will not be excluded from summary tables but will be clearly identified in TEAE listings.

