2.3. Study Endpoints

2.3.1. Primary Endpoints:

Immunogenicity:

- Serotype-specific serum IgG GMCs measured 4 weeks post booster dose

Safety, Tolerability:

- Number and severity of solicited local and systemic adverse events (AEs) through Day 6 post each vaccination
- Number, severity and relatedness of all unsolicited AEs until 9 months of age, and from booster vaccination through 4 week follow-up period.
- Number, severity and relatedness of all serious adverse events (SAEs) through the entire study period

2.3.2. Secondary Endpoints:

For Secondary Objective 1 (post-booster OPA GMTs):

- Serotype-specific serum OPA GMTs measured 4 weeks post booster dose

For Secondary Objective 2 (post-booster seroresponse rates):

- Percentage of subjects with serotype-specific serum IgG concentrations $\geq 0.35 \mu\text{g/mL}$ measured 4 weeks post booster dose
- Percentage of subjects with serotype-specific serum IgG concentrations $\geq 1.0 \mu\text{g/mL}$ measured 4 weeks post booster dose
- Percentage of subjects with serotype-specific serum OPA titers $\geq 1:8$ measured 4 weeks post booster dose

For Secondary Objective 3 (post-primary IgG responses):

- Percentage of subjects with serotype-specific serum IgG concentrations $\geq 0.35 \mu\text{g/mL}$ measured 4 weeks post completion of primary vaccination

- Serotype-specific serum IgG GMCs measured 4 weeks post completion of primary vaccination

For Secondary Objective 4 (post-primary OPA responses):

- Percentage of subjects with serotype-specific serum OPA titers $\geq 1:8$ measured 4 weeks post completion of primary vaccination
- Serotype-specific serum OPA GMTs measured 4 weeks post completion of primary vaccination

For Secondary Objective 5 (persistence of post-primary IgG responses):

- Percentage of subjects with serotype-specific serum IgG concentrations $\geq 0.35 \mu\text{g/mL}$ measured prior to booster dose
- Serotype-specific serum IgG GMCs measured prior to booster dose

For Secondary Objective 6 (persistence of post-primary OPA responses):

- Percentage of subjects with serotype-specific serum OPA titers $\geq 1:8$ measured prior to booster dose
- Serotype-specific serum OPA GMTs measured prior to booster dose

For Secondary Objective 7 (booster effects):

- Ratio of serotype-specific serum IgG GMCs measured 4 weeks post booster dose to serotype-specific IgG GMCs measured 4 weeks post completion of primary vaccination

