12.8. Safety and Tolerability Analyses

AEs will be coded by system organ class and preferred term using the Medical Dictionary for Regulatory Activities (MedDRA) (version 21.0 or later).

The safety and tolerability of study vaccines will be evaluated by tabulating, by treatment group, the severity of solicited local and systemic AEs through Day 6 post each dose; the severity and relatedness of unsolicited AEs through 4 weeks after the booster dose; and the severity and relatedness of SAEs. All tabulations will include both the number of events in a given severity/relatedness category and the number (percentage) of subjects experiencing such events. Results will be tabulated separately through 4 weeks post primary series and through 4 weeks post booster (final analysis). Comparisons of event rates between groups will be made using descriptive 95% CIs and Chi-squared tests stratified on field

site, with no adjustment for multiple comparisons (exact methods will be used if there are fewer than 5 events in one or both groups being compared for a given outcome).

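### The overall unsolicited-AE tables cover more than the primary endpoint's windows, and the pre-booster cut-off is 9 months in some passages and 10 months in others

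*SAP*

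**What the plan says.** **Endpoint.** Protocol 2.3.1 defines the second primary safety endpoint as "Number, severity and relatedness of all unsolicited AEs until 9 months of age, and from booster vaccination through 4 week follow-up period". SAP 2.2.1 and 5.4.1 repeat it: "Number, severity and relatedness of all unsolicited AEs until 9 months of age, and from booster vaccination through a 4-week follow-up period". The window has two segments, with a hole between 9 months and the booster. SAEs have their own endpoint, which covers the whole study.

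**Tables.** SAP 5.4.2 sets the outer limit: "Only TEAEs with onset on or before V6 (4-weeks post booster) will be included in the formal safety analysis". It plans "Summary tables of TEAEs (overall and by onset within 28 days of each vaccination", and uses the same two windows for severity and relatedness. Protocol 12.8 adds one more split: "Results will be tabulated separately through 4 weeks post primary series and through 4 weeks post booster (final analysis".

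**Events in the hole.** SAP 5.4.2 explains that "unsolicited AEs were not routinely collected after 9 months of age but before the booster dose (V5". It then directs that recorded AEs with "onset after 9 months but before V5 will not be excluded from summary tables but will be clearly identified in TEAE listings".

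**Collection.** The Safety Monitoring part of Protocol Section 3 first says AEs are monitored through 9 months of age and again from the booster. The same paragraph then gives a different rule. Infants boosted at 9 (+1) months are monitored for all unsolicited AEs throughout. Infants boosted after 10 months have SAE-only monitoring from 10 months until booster. Protocol 9.2.7 repeats the 10-month rule.

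**Shells.** SAP Sections 1 and 6 place the mock tables in a separate document, which was not available.

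**The concern.** Two things do not line up.

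First, the endpoint leaves out the interval between 9 months and the booster, while the overall tables keep whatever was recorded there. For a late-boosted infant that interval contains fully collected SAEs, fully collected AEs up to 10 months if the protocol's operational rule was followed, and after that only such non-serious AEs as happened to be recorded. The overall count of unsolicited AEs is thus a different quantity from the stated endpoint, and it mixes fully monitored time with SAE-only time. The gap events are marked only in listings, so a reader cannot take the endpoint from any described table.

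Second, the edge of the hole is not settled. AEs between 9 and 10 months are required by Protocol Section 3, lie outside the literal endpoint, and are described in SAP 5.4.2 as not routinely collected. Either required data were not gathered or the SAP misdescribes what was gathered. The study report has to say which.

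At stake are the absolute number of events and percentage of infants with unsolicited AEs, which are a primary safety output, and the meaning of the denominator time behind them.

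**Working it through.** **1. The plan's own figures.** Protocol 12.1 and SAP 3.2.2 use 220 per group. The chance of at least one event at probability 0.01 is 1 − 0.99^220 = 0.890 (stated 89%). The upper bound with no events is 1 − 0.025^(1/220) = 0.0166 (stated 0.017). Both reproduce and neither is in dispute; 220 is the denominator used in step 5.

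The Protocol Summary gives follow-up of about 37 to 73 weeks. With a month of 365.25/12/7 = 4.348 weeks, first vaccination at 6 weeks of age and V6 at 4 weeks after booster, the minimum is 39.1 − 6 + 4 = 37.1 weeks, which agrees. The maximum for a booster at 18 months is 78.3 − 6 + 4 = 76.3 weeks. The stated 73 is recovered with four-week months (37 + 9 × 4). I use calendar months; four-week months would shorten the longest SAE-only gap below from 34.8 to 8 × 4 = 32 weeks.

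**2. Windows side by side.** The endpoint statements give no start, so I take first vaccination from the TEAE definition in SAP 5.4.2.

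| Source | Window | Restricted to the endpoint windows? |
|---|---|---|
| Endpoint (Protocol 2.3.1; SAP 2.2.1, 5.4.1) | to 9 months, plus booster to 4 weeks | – |
| SAP 5.4.2, overall | first vaccination to V6, gap events kept | no: wider |
| SAP 5.4.2, 28-day | 28 days after each dose | no: narrower |
| Protocol 12.8, first | through 4 weeks post primary | no: narrower |
| Protocol 12.8, second | through 4 weeks post booster | no: wider |

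**3. Time per infant, in weeks.** Span = booster age − 6 + 4. Endpoint time = (39.1 − 6) + 4 = 37.1 at every booster age. Time after 9 months = booster age − 39.1. SAE-only time = booster age − 43.5, or zero if the booster is given by 10 months.

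| Booster age | Span V1–V6 | Endpoint | 9 months to booster | of which SAE-only | SAE-only share of span |
|---|---|---|---|---|---|
| 9 mo | 37.1 | 37.1 | 0 | 0 | 0% |
| 10 mo | 41.5 | 37.1 | 4.3 | 0 | 0% |
| 12 mo | 50.2 | 37.1 | 13.0 | 8.7 | 17.3% |
| 15 mo | 63.2 | 37.1 | 26.1 | 21.7 | 34.4% |
| 18 mo | 76.3 | 37.1 | 39.1 | 34.8 | 45.6% |

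The overall window equals the endpoint window only for a booster at exactly 9 months. SAE-only time makes up more than half of the gap once the booster is later than 11 months, since (b − 10)/(b − 9) exceeds one half only when b > 11. These are shares of calendar time, not of events.

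**4. The 9-versus-10-month strip.** Fully monitored time under the 10-month rule is (43.5 − 6) + 4 = 41.5 weeks. The literal endpoint covers 37.1. The difference is 0 to 4.3 weeks for infants boosted between 9 and 10 months and 4.3 weeks for later boosters, at most 4.35/41.5 = 10.5% of monitored time.

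**5. Effect of one event.** Each recorded gap AE adds one event. It moves the percentage with any TEAE by 1/220 = 0.45 points, and only if that infant has no other TEAE. In VAC-056 (Protocol Table 4) upper respiratory infection alone affected 48.6% and 50.7% of the two groups, so many infants would already be counted. Event totals and rows for a single preferred term lack this protection.

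**6. What cannot be computed.** The documents give neither the distribution of booster ages nor the number of gap AEs. SAP 4.1 will report the share with a delayed booster, and Protocol 1.10 plans to boost as many as possible at 9 months.

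**The case against.** The strongest reply is that SAP 5.4.2 leaves nothing open about the tables. Every recorded TEAE with onset by V6 is tabulated, gap events are kept by a disclosed rule, and the SAP appendix says the rule was adopted blind to individual assignments. That stands. Moving the cut-off from 9 to 10 months would not change any described table; it would change only which listing rows are flagged and what the endpoint says. Keeping all recorded safety events is also a defensible choice in itself.

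A reader might infer that the primary endpoint goes unreported. The documents do not support that: the overall tables contain both endpoint segments in full. The defect is that they add to them, and no described table takes the addition out. Such a table may exist in the unseen shells, so the point is limited to the SAP and protocol text.

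It can also be said that 9 months was meant loosely as 9 (+1), the booster window before the pandemic amendment (SAP 5.3.8). That is plausible, but no passage says so, and Protocol Section 3 uses both limits in one paragraph.

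Finally, a reader might see a further rule with no gap at all, since Protocol 9.1 collects AEs through Visit 6 and Protocol 12.8 tabulates "the severity and relatedness of unsolicited AEs through 4 weeks after the booster dose". That reading is weak. Protocol 9.1 is qualified to relevant visits, 9.2.7 states the SAE-only exception explicitly, and 12.8 describes tabulation, not when collection stops. The conflict that remains is 9 against 10 months.

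**Conclusion.** The point holds as a mismatch between endpoint and tables, plus a contradiction in the cut-off. The overall tables report the primary unsolicited-AE endpoint together with incompletely ascertained gap events, and nothing described in the text separates them. The exposed time is nil for boosters at 9 months and up to 4.3 weeks, all fully monitored, for boosters between 9 and 10 months. For later boosters it reaches 39.1 weeks at 18 months, of which 34.8 are SAE-only.

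The effect on counts and percentages is probably small, because few non-serious events are likely to have been recorded while collection was not routine. That is a judgement; the documents give no count. It would be wrong to infer bias between arms: allocation was 1:1:1 within field site, the delays came from the suspension of visits, and the gap rule applies to every arm alike. The matter is worth correcting but does not threaten the safety comparison.

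The figures assume first vaccination at 6 weeks of age, V6 exactly 4 weeks after booster, and calendar months.

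**What to change.** 1. Reconcile the cut-off in Protocol 2.3.1, Section 3 and 9.2.7 and in SAP 2.2.1, 5.4.1 and 5.4.2 to what was actually collected, and state how events between 9 and 10 months are treated.
2. Add a dataset flag for onset after the reconciled cut-off and before booster.
3. Add one summary table of number, severity and relatedness of unsolicited AEs, by arm, restricted to first vaccination up to the cut-off or booster (whichever is earlier) plus booster to 4 weeks after. Show non-serious gap AEs separately, with a note that they were not systematically collected. Keep SAEs for the whole study under their own endpoint.
4. Keep the existing overall and 28-day tables.

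The cost is wording changes, one flag and one table. No new data are needed and nothing already planned is lost. If the shells already hold such a table, citing it in SAP 5.4.2 would cover step 3.
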